9.2 Data Management Plan

The CRFs will be stored in a locked office in the Nuclear Medicine clinic. Records will be kept using OnCore.

During the clinical investigation, the Protocol Director will evaluate the progress of the trial, including periodic assessments of data quality and timeliness, participant recruitment, accrual and retention, participant risk versus benefit, performance of trial sites, and other factors that can affect study

outcome. Monitoring of the trial will occur every 8 weeks and a record of monitoring activities will be maintained by the study team.

The Stanford Cancer Institute Data and Safety Monitoring Committee (DSMC) will audit study related activities to determine whether the study has been conducted in accordance with the protocol, local standard operating procedures, FDA regulations, and Good Clinical Practice (GCP). This may include review of regulatory binders, case report forms, eligibility checklists, and source documents. In addition, the DSMC will regularly review serious adverse events and protocol deviations associated with the research to ensure the protection of human subjects. Results of DSMC audits will be communicated to the IRB and the appropriate regulatory authorities at the time of continuing review, or in an expedited fashion, as needed.

10. Statistical Considerations and Evaluation of Results

10.1 Aim 1

Participants: 100 patients with low- or intermediate-risk prostate cancer, as described in the inclusion/exclusion criteria.

Design: Patients will have both ^{68}Ga -RM2 and ^{68}Ga -PSMA-11 PET/MRI, including mpMRI. mpMRI and PET images will each be evaluated separately. For each of the 12 prostate regions, between 1-3 imaging-positive samples will be taken, and 1 sample will be taken from each imaging-negative region.

Outcome measures: Number and location of lesions will be recorded for each modality in each patient. Gold standard will be based on the biopsy of lesions found on ^{68}Ga -RM2 and ^{68}Ga -PSMA-11 PET and prior systematic prostate biopsy, including IHC stains for GRPr and PSMA.

Hypothesis: ^{68}Ga -RM2 and ^{68}Ga -PSMA-11 PET/MRI sensitivity, either alone or in combination, will be higher than that of mpMRI alone.

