Because there may be multiple lesions per-patient and an indefinite number of non-lesions, the primary analysis will be per-region. Each of the 12 regions will have gold-standard positive or negative information, as well as imaging positive or negative assessments. Predictive accuracy of PI-RADS composite score (mpMRI) and SUV_{\max} PET uptake values will be assessed by ROC analysis using univariable logistic regression for the presence of PC. Areas under the entire ROC curve, and partial area at fixed 90% specificity will be compared. Additional benefit of the other modalities over mpMRI alone will be tested by a multivariable logistic regression. All analyses will be adjusted for clustering within patient.

Statistical Power and Sample Size: Based on our clinical experience at Stanford, we expect an average of 2 PC-positive regions and 10 PC-negative regions per patient. Assuming mpMRI has sensitivity of 80% and specificity of 80-90% [91], a sample size of 1200 regions with 20% prevalence will provide 90% power at 5% error to demonstrate non-inferiority of a PET sensitivity of 90% at 80-90% specificity [62, 92, 93].

The per-lesion analysis will depend on the number of lesions found but will be similar. We will also explore whether specific imaging findings are especially accurate in detection of specific subtypes of PC or prostate regions (i.e., peripheral versus transitional zones). It may also be the case that

predictive failures in imaging may be associated with a particular subtype. Given the small sample, we acknowledge that this analysis will be exploratory.

10.2 Aim 2

Participants: Those enrolled in Aim 1.

Design: Patients will be scanned with both ⁶⁸Ga-RM2 PET/MRI and ⁶⁸Ga-PSMA-11 PET/MRI at six months after initiation of therapy. MRI and PET images will each be evaluated separately.

Outcome measures: Changes in MRI features and/or changes in radiopharmaceutical uptake in lesions will be recorded for each modality in each patient. Gold standard of response to treatment and of PFS will be based on standard clinical follow-up (PSA, imaging, tissue diagnosis including IHC stains for GRPr and PSMA)

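### Aim 1 power rests on 20% prevalence (240 positive regions), but the same paragraph expects 2 of 12 regions positive (16.7%, 200), so the stated 90% needs to be recomputed

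*Combined protocol and SAP*

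**What the plan says.** Section 10.1 of the combined protocol and SAP describes Aim 1 as "Participants: 100 patients with low- or intermediate-risk prostate cancer". Under Statistical Analysis it states that "the primary analysis will be per-region. Each of the 12 regions will have gold-standard positive or negative information", so 100 patients contribute 100 × 12 = 1200 regions.

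The paragraph on Statistical Power and Sample Size then gives two figures for how many regions are positive. Its first sentence reads "we expect an average of 2 PC-positive regions and 10 PC-negative regions per patient". Its second states that "a sample size of 1200 regions with 20% prevalence will provide 90% power at 5% error". The assumed sensitivities are 80% for mpMRI and 90% for PET. The claim is 90% power at 5% error "to demonstrate non-inferiority of a PET sensitivity of 90% at 80-90% specificity".

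Three further points bear on the reading:

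- The Aim 1 hypothesis, earlier in Section 10.1, is that PET/MRI sensitivity exceeds that of mpMRI alone. That is superiority, not non-inferiority.
- The plan says that all analyses adjust for clustering within patient, but the power statement reports no intracluster correlation or design effect.
- The 5% is not described as one- or two-sided. The Aim 2 power statements in Section 10.2 are explicitly one-sided.

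**The concern.** Two of 12 is one sixth, not one fifth. Sensitivity is estimated only in regions that are positive on the reference standard, so the number of positives, not the 1200 regions, drives the power. The power statement credits the trial with 40 more positives than the preceding sentence expects. At 2 per patient, 240 positives would need 120 patients.

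At stake is whether the stated power for the main sensitivity comparison follows from the plan's own expectations. The negatives are not a difficulty: they rise from 960 to 1000, so specificity is estimated slightly better.

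**Working it through.** **Inputs from Section 10.1.** 100 patients; 12 regions each; 2 positive regions expected per patient; 20% prevalence in the power sentence; sensitivities 0.80 (mpMRI) and 0.90 (PET), so δ = 0.10; 5% error; 90% power. **Not given, so assumed below:** sidedness, non-inferiority margin, correlation of PET and mpMRI errors, design effect.

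**1. Counts.** 1200 × 0.20 = 240 positives (2.4 per patient). 100 × 2 = 200 positives (2/12 = 16.7%). 240/200 = 1.20, an inflation of 20%.

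**2. Reproducing the 90%.** Take a zero margin, one-sided 5%, readings treated as independent and no clustering. With mean sensitivity 0.85:

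n₀ = [1.645·√(2·0.85·0.15) + 1.282·√(0.16 + 0.09)]² / 0.10² = 217 after rounding up.

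With the continuity correction, n = (n₀/4)·[1 + √(1 + 4/(n₀δ))]² = 237, close to 240. To get the power at a given n, invert the correction, n₀ = n − 2/δ + 1/(nδ²), and use Φ{(δ√n₀ − 1.645·√0.255)/√0.25}:

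- n = 240: n₀ = 220.4, Φ(1.308) = 90.5%.
- n = 200: n₀ = 180.5, Φ(1.026) = 84.8%.

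Other zero-margin variants at 240 fit less well. Without the correction, power is 92.5% one-sided and 86.8% two-sided (87.8% and 80.2% at 200). With it, two-sided power is 83.9%.

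**3. Check that does not depend on the test.** If 90% is the exact power at 240 under any normal-approximation test, multiply the standardised effect by √(200/240) = 0.913:

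- One-sided 5%: (1.645 + 1.282)·0.913 − 1.645 = 1.026, power 84.8%.
- Two-sided 5%: (1.960 + 1.282)·0.913 − 1.960 = 0.999, power 84.1%.

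If 90% is only a floor, this loss need not take the power below it.

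**4. Paired comparison, zero margin.** PET and mpMRI are read on the same regions, so a McNemar-type calculation is a natural alternative. With error correlation φ, discordance is ψ = 0.26 − 0.24φ and power is Φ{(0.10·√n − z·√ψ)/√(ψ − 0.01)}, where n is divided by the design effect (DE). With 2 positives per patient, DE = 1 + intracluster correlation, so the assumed DEs of 1.1 and 1.3 correspond to correlations of 0.1 and 0.3.

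| Positives | DE | φ = 0, one-sided | φ = 0, two-sided | φ = 0.3, one-sided |
|---|---|---|---|---|
| 240 | 1.0 | 92.2% | 86.4% | 97.6% |
| 200 | 1.0 | 87.5% | 79.7% | 95.2% |
| 200 | 1.1 | 84.6% | 75.7% | 93.4% |
| 200 | 1.3 | 78.9% | 68.5% | 89.4% |

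At φ = 0.1, 200 positives and no clustering, one-sided power is 90.2%. At φ = 0.3, two-sided power without clustering is 91%.

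**5. Non-inferiority taken literally, with an assumed margin m.** With 200 positives and independent errors, power is Φ{(0.10 + m)/√(0.25·DE/200) − z}:

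- m = 2 points, no clustering: 96% at one-sided 5%, 92% at one-sided 2.5%.
- m = 5 points, no clustering: 99.5% and 98.9%.
- m = 5 points, DE 1.3: 98% and 96%.

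Without clustering, a margin of about 0.35 points (one-sided 5%) or 1.5 points (one-sided 2.5%) is enough for 90%. With an assumed DE of 1.5, about 2.7 or 4.0 points are needed.

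**The case against.** A reader might infer that the true power is below 90%, or that the trial is too small. The documents do not support that. The sentence claims non-inferiority, and no margin is given, so the stated 90% cannot be checked as worded. With 200 positives a small margin restores 90% (step 5), and so can modest positive correlation between PET and mpMRI errors on a paired zero-margin test (step 4). The lowest figures in step 4 need independent errors, a two-sided test and an assumed design effect together, none of which the plan specifies for Aim 1. Nor is a McNemar test named for Aim 1; the listed analyses are ROC areas and clustered logistic regression.

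A reader might also infer that the calculation treated regions as independent. No formula is shown, so all that can be said is that no clustering allowance is reported.

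Finally, 20% may be a rounding of 16.7%. That would explain the discrepancy but not remove it: the rounding still adds 40 positives.

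These objections stand as limits on the size of the effect. They leave the two counts irreconcilable as written. A favourable non-inferiority margin also does not help the Aim 1 hypothesis, which is superiority and so a zero-margin question.

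**Conclusion.** The inconsistency is certain: adjoining sentences imply 200 and 240 positive regions, and the power uses the larger, 20% above the plan's own expectation. Fewer positives mean less power for sensitivity under any test.

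The effect on power is conditional. On the zero-margin, one-sided 5%, continuity-corrected calculation that reproduces the 90%, it drops from 90.5% to 84.8%, before any allowance for clustering. Whether actual power is below 90% is undetermined, because margin, sidedness, discordance and design effect are all unstated. The correction is worth making before analysis, but it is a restatement of the power, not evidence that the trial is underpowered.

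**What to change.** In the power paragraph of Section 10.1:

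- Recompute and restate the power with 200 positive regions (16.7%).
- Align the power statement with the superiority hypothesis of Aim 1. If non-inferiority is intended, state the margin.
- State whether the 5% is one- or two-sided.
- Report power over an assumed range of PET-mpMRI error correlation and of within-patient design effect (for example 1.0 to 1.3), labelled as assumptions.

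The sample size should stay at 100 patients. The cost is a rewritten paragraph and one recalculation; the downside is a stated power that may be somewhat less favourable. Trial conduct is unaffected.

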5.3 Image interpretation

The PET/MRI scans will be interpreted by ABNM certified Nuclear Medicine physicians and ABR certified Radiologists. Drs [name], [name], [name] and [name] have significant clinical experience and will be blinded to the participants' medical history and the results of other imaging modalities. Consensus read will be obtained for each scan. Each lesion will be tabulated and a comparison of lesion detection by each tracer will be conducted.

The study team will communicate the results of the scans to the referring (treating) physicians.

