Reference standard: disease status of a lesion will be defined by biopsy of lesions found on ^{68}Ga -RM2 and ^{68}Ga -PSMA-11 PET and from prior saturation prostate biopsy. Tissue samples will be evaluated for GRPr and PSMA expression as previously reported [1, 2] and results will be compared to imaging findings. For GRPr staining, immunohistochemistry will be performed using standard protocols with primary rabbit polyclonal antibody (OPA1-15619, 1:200 dilution; Affinity Bioreagents, Golden, Colorado). For PSMA, a rabbit polyclonal anti-PSMA antibody (D7I8E; Cell Signaling technology, #12815, 1:100 dilution) will be used following the manufacturer's immunohistochemistry protocol. We already successfully used

these, as shown on page 11.

Drs. [name] (clinical pathologist), [name] and [name] will perform all histopathological analyses. Clinical follow-up will be gold standard if biopsy cannot be done.

Test to be evaluated: All T1w, T2w, DWI and DCE MR images will first be analyzed and graded by two-board certified abdominal radiologists with subspecialty training in body MRI and extensive clinical experience in prostate MRI (Drs. [name] and [name]) using the PI-RADS version 2 scoring system, blinded to the clinical information and pathology. The PET images will be corrected using the attenuation data from the MRI scan, and Drs. [name] and [name] who already have extensive experience with ^{68}Ga -RM2 and ^{68}Ga -PSMA-11 from our clinical trials, will perform blinded and random interpretation of the PET scans. Areas of focally increased ^{68}Ga -RM2 and ^{68}Ga -PSMA-11 uptake above surrounding background will be considered positive for PC (**Figures 9 and 10**). This approach is based on recently published guidelines for standard image interpretation developed for ^{68}Ga -PSMA-11 image interpretation [90]. In addition, semi-quantitative measurements of tracer uptake (SUV_{\max}) will be recorded for each lesion.

Statistical Analysis: The following statistical considerations have the full support of a biostatistician ([name]) within the Department of Radiology, who has been specifically assigned to the project and can provide continuous support throughout the data collection and data analysis process. He has also carefully reviewed the study design and was fully involved in the writing of this grant proposal.

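### The Aim 1 per-lesion analysis has no defined negatives, so its specificity and ROC areas depend on which modality marked the lesions and are not comparable with the per-region results

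*Combined protocol and SAP*

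**What the plan says.** All of this is in section 10.1 (Aim 1) unless stated.

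- **Unit of analysis.** "Because there may be multiple lesions per-patient and an indefinite number of non-lesions, the primary analysis will be per-region".
- **Per-region method.** PI-RADS score and SUVmax "will be assessed by ROC analysis using univariable logistic regression for the presence of PC". Then: "Areas under the entire ROC curve, and partial area at fixed 90% specificity will be compared". A multivariable logistic model tests what is gained over mpMRI, with adjustment for clustering within patient.
- **Per-lesion method, in full.** "The per-lesion analysis will depend on the number of lesions found but will be similar". No candidate-lesion list, matching rule or lesion-level negative is given.
- **Lesion truth.** The Reference standard paragraph says "disease status of a lesion will be defined by biopsy of lesions found on" the two PET scans, and "from prior saturation prostate biopsy". Lesions seen only on mpMRI are not named. Clinical follow-up stands in where biopsy is impossible.
- **Sampling.** The Design paragraph says that in each of 12 regions "between 1-3 imaging-positive samples will be taken, and 1 sample will be taken from each imaging-negative region". Here imaging is not limited to PET.
- **Use of lesions.** Section 5.3: "Each lesion will be tabulated and a comparison of lesion detection by each tracer will be conducted".

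**The concern.** ROC area, specificity and logistic regression for the presence of cancer all need a set of negatives that was not chosen by the test being judged. The plan recognises that lesions offer no such set and moves to regions for that reason. It then carries the same method back to lesions.

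Under the Reference standard paragraph, a benign lesion enters the data only because PET marked it. A PET-negative lesion enters only because biopsy had already shown cancer. Benign cores from the prior biopsy, and the single sample from each imaging-negative region, supply negative regions but not negative lesions.

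The negatives are thus PET's own false positives, while mpMRI is judged on sites that it did not choose. The comparison is tilted against PET before any data arrive. The general aim, finding cancers beyond mpMRI, is naturally discussed lesion by lesion, so a lesion-level ROC result that contradicts the per-region one could be taken as evidence when it is an artefact of selection.

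**Working it through.** **Plan's own figure.** The per-lesion analysis has none. The per-region figure is 1200 regions at 20% prevalence (240 positive), sensitivity 80% against 90%, 90% power, 5% error. An unpaired one-sided comparison with continuity correction and no clustering needs 237 positives; 237/0.20 = 1185, close to 1200. This does not bear on the lesion problem.

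**Inputs (section 10.1).** 2 positive and 10 negative regions per man, so 200 and 1000 in 100 men; PET sensitivity 90%, specificity 80-90%; mpMRI sensitivity 80%, specificity 80-90%.

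**Assumptions, not in the plan.** One candidate lesion per region; every PET-missed cancer known from prior biopsy; errors independent between modalities unless stated; scores normal with equal variance in cancer and non-cancer; PET treated as one score in steps 1 and 2.

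**Step 1: yes/no combined-PET call, PET-found lesions plus known cancers.** True positives 0.9 × 200 = 180; missed 20; false positives 1000 × 0.10 to 0.20 = 100 to 200; true negatives 0. Specificity is 0/(100 to 200) = 0%. What these data can give is positive predictive value, 180/280 = 64% to 180/380 = 47%, and 1 to 2 false-positive marks per man.

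**Step 2: SUVmax in the same set.** Separation d = z(sens) + z(spec); region area A = Φ(d/√2). Benign lesions are those above the threshold t = z(spec), so the lesion area is A_t = ∫ φ(x)Φ(d − x)dx over x > t, divided by (1 − spec).

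| Test | d | Region area | Lesion area |
|---|---|---|---|
| PET 90%/90% | 2.563 | 0.965 | 0.775 |
| PET 90%/80% | 2.123 | 0.933 | 0.748 |
| mpMRI 80%/90% | 2.123 | 0.933 | 0.933 |
| mpMRI 80%/80% | 1.683 | 0.883 | 0.883 |

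Per region, PET is better than mpMRI in three of the four specificity pairings and equal in one. In the lesion set mpMRI is better in all four. If PET-missed cancers are dropped for want of an SUVmax, the PET area is 0.83-0.86, still below mpMRI.

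**Step 3: partial area.** Lesion-level 90% specificity corresponds to region-level 1 − (1 − spec) × 0.1, that is 98% to 99%. The two partial areas describe different parts of the curve.

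**Step 4: one tracer among the marks of both.** With each tracer at the PET figures, specificity is 1 − (1 − sp)/(1 − sp²): 1 − 0.1/0.19 = 47% and 1 − 0.2/0.36 = 44%.

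**Step 5: mpMRI-only marks also biopsied.** Take two tests equal per region (PET 90%/80%, mpMRI 80%/90%, both 0.933). The share of benign lesions that a test marked is w = (1 − sp)/(1 − 0.8 × 0.9): PET 0.2/0.28 = 0.714, mpMRI 0.1/0.28 = 0.357. Specificities are 29% and 64%. The yes/no areas are (0.90 + 0.286)/2 = 0.59 and (0.80 + 0.643)/2 = 0.72.

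For the scores, the area against unmarked negatives is A_u = [A − (1 − sp)A_t]/sp and the lesion area is wA_t + (1 − w)A_u:
- PET: A_u = (0.933 − 0.2 × 0.748)/0.8 = 0.980; 0.714 × 0.748 + 0.286 × 0.980 = 0.81.
- mpMRI: A_t = 0.638; A_u = (0.933 − 0.1 × 0.638)/0.9 = 0.966; 0.357 × 0.638 + 0.643 × 0.966 = 0.85.

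Equal tests no longer look equal, and the one that makes fewer false marks gains.

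**The case against.** A reader might go further and infer that PET's lesion-level specificity is 0% by construction in any analysis and that its odds ratio for cancer turns below 1. The documents do not support that, for three reasons.

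- **Predictor.** The plan models SUVmax, not a yes/no mark. In the step 2 set its odds ratio per SD stays at 3.4-3.6, or 2.2-2.8 if missed cancers are given the background value. The area is reduced but there is no reversal.
- **Two tracers.** The tracers are compared separately. A benign lesion marked by PSMA-11 alone is a true negative for RM2. If a share s of each tracer's false positives is common to both, and they have equal false-positive rates, specificity is (1 − s)/(2 − s) and the odds ratio is 9(1 − s). At s = 0.5 these are 33% and 4.5. The odds ratio falls below 1 only when s exceeds 8/9, about 89%.
- **Sampling.** The Design paragraph takes samples at imaging-positive sites without limiting them to PET, and clinical follow-up can stand in for biopsy. A benign mpMRI-only lesion may therefore have a reference status, which brings in PET-negative benign lesions.

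The analysis is also not primary. The endpoints in sections 2.5 and 10.3 count participants with an assessable result, the Aim 1 hypothesis concerns sensitivity, and comparing detection by tracer needs no true negatives. The sentence on the per-lesion analysis sits under the sample-size heading and may refer partly to power.

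These points narrow the scope and lower the severity. They do not supply a lesion-level negative set, and steps 4 and 5 show that the more generous readings still leave specificity and area dependent on who made the marks. The remark that an analysis is exploratory follows the sentences on subtype and zone and does not clearly cover this one.

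**Conclusion.** The point holds in limited form. Lesion-level specificity, ROC area and the partial area at 90% specificity depend on which modality marked the lesions and cannot be set beside the per-region results. The 0% specificity applies only to a yes/no, combined-PET call under the Reference standard paragraph as worded. For SUVmax there is no reversed odds ratio, but the order of PET and mpMRI can reverse through selection alone. The bias is smaller if mpMRI-only marks are biopsied or tracers are judged singly.

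The areas rest on the assumptions listed in the working; the direction of the bias under the Reference standard wording is less sensitive to them than its size. Because no primary conclusion rests on this analysis, the severity is minor to moderate.

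**What to change.** Replace the sentence on the per-lesion analysis with text that:

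1. defines the candidate-lesion set as all lesions marked by any modality plus all biopsy-proven cancers;
2. reports sensitivity of each modality over all biopsy-proven cancers, compared as paired data with patient-clustered intervals;
3. reports positive predictive value of marks and false-positive marks per man, with a free-response ROC if a curve is wanted;
4. states that specificity, ROC area, partial area and logistic regression for cancer are done at region level only.

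The Reference standard paragraph should then name mpMRI-only lesions, so that it agrees with the sampling in the Design paragraph. The cost is one or two SAP sentences, plus that wording change, and the loss of a conventional lesion-level ROC area. The sampling already described covers imaging-positive sites, so no new data are needed.

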Test to be evaluated: All T1w, T2w, DWI and DCE MR images will first be analyzed and graded by two-board certified abdominal radiologists with subspecialty training in body MRI and extensive clinical experience in prostate MRI (Drs. [name] and [name]), before and after treatment. Areas of focally increased ⁶⁸Ga-RM2 or ⁶⁸Ga-PSMA-11 uptake above surrounding background on pre-therapy scans will be evaluated for changes in uptake by Drs. [name] and [name].

Hypotheses

Primary: Change in ⁶⁸Ga-RM2 or ⁶⁸Ga-PSMA-11 uptake from baseline (T0) to 6 months after start of treatment (T1) will predict treatment response better than T0-T1 changes in MRI.

Secondary: T0-T1 change in ⁶⁸Ga-RM2 or ⁶⁸Ga-PSMA-11 uptake will predict progression-free survival (PFS) better than MRI.

Statistical Analysis:

Primary: (a) logistic regression of response/non-response at T6 on T1-T0 change in PET/MRI measures; (b) McNemar tests of MRI and PET predictions of T6 response.

Secondary: (a) log-rank tests of PFS time (length of drug response) on patients dichotomized as above/below the median change in PET/MRI measures; (b) Cox proportional-hazards regressions of PFS on amount of T1-T0 change in PET/MRI measures.

Statistical Power and Sample Size: We expect a 70-80% response rate to treatment, and 20% of responders progressing by two years.

A sample size of ~75 responders and ~25 non-responders will provide 90% power at one-sided 5% error to detect sensitivity low as 80% at fixed 90% specificity, and to demonstrate a difference in sensitivities of 10 percentage points (e.g., 80% vs 90%).

Median-change groups of ~40 each among the responders will provide 90% power at one-sided 5% error to detect differences in PFS hazard ratios as small as 2.5.

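### Aim 2: the logistic regression listed as a primary analysis does not test whether PET predicts response better than MRI, so only a paired PET-versus-MRI comparison should decide that hypothesis

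*Combined protocol and SAP*

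**What the plan says.** Under Hypotheses in section 10.2, the primary statement is that change in RM2 or PSMA-11 uptake between baseline (T0) and six months (T1) "will predict treatment response better than T0-T1 changes in MRI". Under Statistical Analysis, the entry marked primary reads "a) logistic regression of response/non-response at T6 on T1-T0 change in PET/MRI measures; (b) McNemar tests of MRI and PET predictions".

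The section does not say which of the two decides, whether one or both must be positive, or which coefficient in (a) is tested. It does not define T6, set cut-offs for a PET or MRI prediction, or say how the two tracers share the error rate.

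The power paragraph takes some 75 patients to respond and some 25 not to, and claims that these numbers "will provide 90% power at one-sided 5% error to detect sensitivity low as 80% at fixed 90% specificity". It adds that the same sample can show a 10-point difference in sensitivity, 80% against 90%. It names no test.

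**The concern.** The hypothesis compares two markers measured in the same patients. McNemar in (b) makes that comparison. The regression in (a) does not. Fitted to PET change alone, its null is that PET change is unrelated to response. Fitted to PET and MRI change together, its null is that PET adds nothing to MRI. Two equally good markers with partly independent errors will normally each add to the other, so a significant PET term in either model is compatible with PET being equal to MRI, or worse.

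Because (a) is labelled primary and its role is not limited, a report could present a significant regression as support for superiority over MRI. That would be most tempting if the McNemar test missed, which the power calculation below shows is quite likely.

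**Working it through.** **Inputs from section 10.2:** about 75 responders and 25 non-responders, 80% sensitivity at 90% specificity, 80% versus 90% as the difference of interest, one-sided 5%.

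**Assumptions not in the documents:** normally distributed change scores in each class; PET-MRI correlation within class of 0 to 0.9; responders as the positive class.

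**Step 1: the plan's 90% power.** Let r be the correlation between PET and MRI being correct in a responder.
- Both correct: p11 = 0.8 × 0.9 + r × √(0.8 × 0.2 × 0.9 × 0.1) = 0.72 + 0.12r.
- Discordant proportion: ψ = 0.8 + 0.9 − 2 × p11 = 0.26 − 0.24r. Difference: δ = 0.10.
- Asymptotic McNemar power = Φ[(δ√n − 1.645√ψ) / √(ψ − δ²)], with n = 75.

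| r | ψ | Asymptotic | Exact |
|---|---|---|---|
| 0 | 0.260 | Φ[(0.866 − 0.839)/0.500] = 52% | 45% |
| 0.4 | 0.164 | Φ[(0.866 − 0.666)/0.392] = 69% | 61% |
| 2/3 (largest possible) | 0.100 | Φ[(0.866 − 0.520)/0.300] = 88% | 88% |

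The last row requires PET to be correct in every responder in whom MRI is correct. So 90% is not reached with 75 responders. An unpaired comparison of 75 per group gives 53%. Only with all 100 patients as denominator does the figure appear (91% at r = 0.6). With the 25 as denominator, power is 10-47%.

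**Step 2: what (a) does when PET equals MRI.** The separation between classes that gives 80% sensitivity at 90% specificity is z(0.80) + z(0.90) = 0.842 + 1.282 = 2.12. The ROC area is Φ(2.12/√2) = 0.933. Both markers get this value. Tests are one-sided at 5%, with 2,000 to 3,000 or more simulated trials per setting.

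| Analysis | Share of trials positive, PET and MRI equal |
|---|---|
| (a) PET alone | 100% |
| (a) PET adjusted for MRI, correlation 0 / 0.5 / 0.7 / 0.9 | 99.8% / 96% / about 80% / 37-42% |
| (b) McNemar, asymptotic, cut-offs known | about 5% |
| Paired difference in ROC area | 4-5% |
| McNemar in responders, each cut-off set at the 90th percentile of the trial's own 25 non-responders | about 20% (19-21%) |

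**Step 3: PET truly worse.** With PET at 70% and MRI at 80% sensitivity (correlation 0.5), PET alone is still significant in 100% of trials and PET adjusted for MRI in 80%. McNemar with known cut-offs is positive in 0.1%.

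**Step 4: weaker but equal markers.** PET alone is positive in 99%, 94%, 76% and 47-49% of trials at ROC areas of 0.75, 0.70, 0.65 and 0.60.

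**Step 5: two tracers joined by or.** If either tracer may win by unadjusted McNemar (correct classification in all 100 patients, known cut-offs, correlation 0 to 0.7, 70 to 80 responders), the false-positive rate is 7.6-9.8%.

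**The case against.** The strongest reply is that (a) and (b) are stages of one analysis. McNemar needs yes/no predictions, and the regression in (a) is the only stated source for them. Aim 1 (section 10.1) uses univariable logistic regression in this way, as the basis for ROC areas that are then compared. The power paragraph also has two parts, one about a single marker and one about a difference, and its one-sided 5% covers the difference. This reading is plausible and the text does not exclude it.

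A reader might infer that the plan has a false-positive rate near 100% for its primary claim. The documents do not support that. They nowhere say that a positive (a) is enough, so the rates in Step 2 are error rates only if it is allowed to count. Nor is (a) almost always positive without conditions: the rate depends on the plan's accuracy figures, and drops when PET and MRI are highly correlated or both weak. The Background (Efficacy assessment) itself notes that MRI is harder to read after treatment.

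It is also true that the endpoints in section 2.5 and the outcomes in section 10.3 are counts of participants with an assessable scan, so the registered outcomes do not turn on this test.

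What stands is that (a) is labelled primary for a superiority hypothesis it does not test, and nothing confines it to producing predictions.

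**Conclusion.** The point holds in this form: (a) does not have PET no better than MRI as its null and should not be able to decide the primary hypothesis of Aim 2. If it were allowed to, equal markers at the plan's own accuracy would meet the hypothesis in 100% of trials for PET alone, and in about 100% down to 37-42% for PET adjusted for MRI. These figures rest on binormal scores, a 75/25 split and the assumed correlations.

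It would be wrong to infer that making (b) the sole test settles matters as it stands. McNemar keeps its 5% only with cut-offs fixed beforehand, the two-tracer rule is open, and its power is below the stated 90% in 75 responders at every possible correlation.

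**What to change.** In section 10.2:

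1. State that only a paired PET-versus-MRI comparison decides the primary hypothesis. Choose one: the paired difference in ROC area between PET change and MRI change, or McNemar among responders with both cut-offs fixed before the data are seen. Cut-offs should not be taken from the trial's own 25 or so non-responders unless the test allows for that.
2. Relabel (a) as supportive, showing association or added value over MRI and not superiority. If it is meant to generate the predictions used in (b), say so.
3. State how RM2 and PSMA-11 share the one-sided 5%, for example by a fixed order or a split.
4. Define T6, and restate the power for the chosen test, its denominator and an assumed discordance. For McNemar in 75 responders this is about 45-70% at error correlations of 0 to 0.4 and at most 88%. Power for the ROC-area difference was not calculated here and needs its own calculation.

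The cost is a few sentences and a new power calculation; no data collection changes. The downsides are that a significant association no longer meets the primary hypothesis, that sharing the error rate between tracers may lower power further, and that the plan must admit less than 90% power if McNemar in responders is kept.
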